9.6 Safety and Adverse events

9.6.1 Definitions

Unanticipated Problem (UP): Any incident, experience, or outcome that meets **all** of the following criteria:

- 1) unexpected (in terms of nature, severity, or frequency) given a) the research procedures that are described in the protocol-related documents, such as the IRB-approved research protocol and informed consent document; and b) the characteristics of the subject population being studied;
- 2) related or possibly related to participation in the research; and
- 3) suggests that the research places subjects or others at a greater risk of harm (including physical, psychological, economic, or social harm) than was previously known or recognized.

Possibly related to participation in the research: There is a reasonable possibility that the AE, experience, or outcome may have been caused by the procedures involved in the research.

Adverse event (AE): Any symptom, sign, illness or experience that develops or worsens in severity during the course of the study. Intercurrent illnesses or injuries should be regarded as AEs. Abnormal results of diagnostic procedures are considered to be AEs if the abnormality:

- results in study withdrawal
- is associated with a serious AE
- is associated with clinical signs or symptoms
- leads to additional treatment or to further diagnostic tests
- is considered by the investigator to be of clinical significance

Serious adverse event (SAE): Adverse reactions are classified as serious or non-serious. A **serious adverse event** is any AE that is:

- fatal
- life-threatening

- requires or prolongs hospital stay
- results in persistent or significant disability or incapacity
- a congenital anomaly or birth defect
- an important medical event

Important medical events are those that may not be immediately life threatening, but are clearly of major clinical significance. They may jeopardize the subject, and may require intervention to prevent one of the other serious outcomes noted above. For example, drug overdose or abuse, a seizure that did not result in in-subject hospitalization or intensive treatment of bronchospasm in an emergency department would typically be considered serious.

All AEs that do not meet any of the criteria for serious should be regarded as ***non-serious AEs***.

9.6.2. Classifying AEs

Severity

The intensity of clinical AEs is graded on a three-point scale – mild, moderate, severe – and is reported on specific AE pages of the CRF.

If the intensity of an AE worsens during study drug administration, only the worst intensity should be reported on the AE page. If the AE lessens in intensity, no change in the severity is required.

The three categories of intensity are defined as follows:

- **Mild** - The event may be noticeable to the subject. It does not influence daily activities, and usually does not require intervention.
- **Moderate** - The event may make the subject uncomfortable. Performance of daily activities may be influenced, and intervention may be needed.
- **Severe** - The event may cause noticeable discomfort, and usually interferes with daily activities. The subject may not be able to continue in the study, and treatment or intervention is usually needed.

Expectedness

AEs must be assessed as to whether they were expected to occur or were unexpected, meaning not anticipated based on current knowledge found in the protocol, investigator brochure, product insert, or label.

Expected: an AE known to be associated with the intervention or condition under study.

OHRP defines an **unexpected AE** as any AE occurring in one or more subjects participating in a research protocol, the nature, severity, or frequency of which is **not** consistent with either:

- 1) the known or foreseeable risk of AEs associated with the procedures involved in the research that are described in a) the protocol-related documents, such as the IRB-approved research protocol, any applicable investigator brochure, and the current IRB-approved informed consent document, and b) other relevant sources of information, such as product labeling and package inserts; or
- 2) the expected natural progression of any underlying disease, disorder, or condition of the subject(s) experiencing the AE and the subject's predisposing risk factor profile for the AE.

Relatedness

- 1) Definite:** the AE is clearly related to the intervention
- 2) Probably:** the AE is likely related to the intervention
- 3) Possible:** the AE may be related to the intervention
- 4) Unlikely:** the AE is doubtfully related to the intervention
- 5) Unrelated:** the AE is clearly not related to the intervention

For each identified AE, an AE form will be completed. Reporting procedures should be started immediately upon learning of a SAE.

9.6.3 Interpretation of definitions

AE Reporting Period

The study period during which AEs must be reported is normally defined as the period from the initiation of any study procedures to the end of the study treatment follow-up at week 12.

Preexisting Condition

A preexisting condition is one that is present at the start of the study. A preexisting condition should be recorded as an AE if the frequency, intensity, or the character of the condition worsens during the study period.

General Physical Examination Findings

At screening, any clinically significant abnormality should be recorded as a preexisting condition. At the end of the study, any new clinically significant findings/abnormalities that meet the definition of an AE must also be recorded and documented as an AE.

Post-study AE

All unresolved AEs should be followed by the investigator until the events are resolved, the subject is lost to follow-up, or the AE is otherwise explained. At the last scheduled visit, the investigator should instruct each subject to report any subsequent event(s) that the subject, or the subject's personal physician, believes might reasonably be related to participation in this study. The investigator should notify the study sponsor of

any death or AE occurring at any time after a subject has discontinued or terminated study participation that may reasonably be related to this study. The sponsor should also be notified if the investigator should become aware of the development of cancer or of a congenital anomaly in a subsequently conceived offspring of a subject that has participated in this study.

Abnormal Laboratory Values

A clinical laboratory abnormality should be documented as an AE if any one of the following conditions is met:

- The laboratory abnormality is not otherwise refuted by a repeat test to confirm the abnormality
- The abnormality suggests a disease and/or organ toxicity
- The abnormality is of a degree that requires active management; e.g. change of dose, discontinuation of the drug, more frequent follow-up assessments, further diagnostic investigation, etc.

Hospitalization, Prolonged Hospitalization or Surgery

Any AE that results in hospitalization or prolonged hospitalization should be documented and reported as a serious AE unless specifically instructed otherwise in this protocol. Any condition responsible for surgery should be documented as an AE if the condition meets the criteria for an AE.

Neither the condition, hospitalization, prolonged hospitalization, nor surgery are reported as an AE in the following circumstances:

- Hospitalization or prolonged hospitalization for diagnostic or elective surgical procedures for a preexisting condition. Surgery should **not** be reported as an outcome of an AE if the purpose of the surgery was elective or diagnostic and the outcome was uneventful.
- Hospitalization or prolonged hospitalization required to allow efficacy measurement for the study.
- Hospitalization or prolonged hospitalization for therapy of the target disease of the study, unless it is a worsening or increase in frequency of hospital admissions as judged by the clinical investigator.

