**Estrogen Receptor Antagonist in Patients with
Pulmonary Arterial Hypertension
(ERA PAH)**

Protocol

July 18, 2016

Version 1.0

**[name], MS
Perelman School of Medicine at the
University of Pennsylvania
Principal Investigator**

Protocol Summary

OBJECTIVES:

- To determine changes in circulating hematopoietic progenitor cells, plasma hormone levels, NT-proBNP, and other plasma biomarkers after the administration of fulvestrant in subjects with pulmonary arterial hypertension.
- To observe changes in tricuspid annular plane systolic excursion, stroke volume index, right ventricular fractional area change, and other echo parameters after fulvestrant administration.
- To determine changes in distance walked in six minutes after fulvestrant administration.
- Safety and side effects associated with fulvestrant administration in subjects with pulmonary arterial hypertension.

STUDY DESIGN:

Phase II single-arm, open-label study of fulvestrant in five post-menopausal women with pulmonary arterial hypertension for twelve weeks.

STUDY POPULATION:**Inclusion criteria:**

- Previous documentation of mean pulmonary artery pressure > 25 mm Hg with a pulmonary capillary wedge pressure (or left ventricular end-diastolic pressure) < 16 mm Hg and pulmonary vascular resistance > 3 WU at any time before study entry.
- Diagnosis of PAH which is idiopathic, heritable, drug- or toxin-induced, or associated with connective tissue disease, congenital heart disease, portal hypertension, or HIV infection.
- Most recent pulmonary function tests with FEV1/FVC >50% AND either a) total lung capacity > 70% predicted or b) total lung capacity between 60% and 70% predicted with no more than mild interstitial lung disease on computerized tomography scan of the chest.
- Female, post-menopausal state, defined as:
 - > 50 years old and a) have not menstruated during the preceding 12 months or b) have follicle-stimulating hormone (FSH) levels > 40 IU/L **or**
 - < 50 years and FSH > 40 IU/L **or**
 - having had a bilateral oophorectomy.
- Informed consent.

Exclusion criteria:

- Age < 18.
- Treatment with estrogen or anti-hormone therapy (tamoxifen, anastrozole, etc.)
- WHO Class IV functional status.
- History of breast cancer.
- Clinically significant untreated sleep apnea.
- Left-sided valvular disease (more than moderate mitral valve stenosis or insufficiency or aortic stenosis or

insufficiency), pulmonary artery or valve stenosis, or ejection fraction < 45% on echocardiography.

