- Initiation of PAH therapy (prostacyclin analogues or receptor agonists, endothelin-1 receptor antagonists, phosphodiesterase-5 inhibitors, soluble guanylate cyclase stimulators) within three months of enrollment; the dose must be stable for at least 3 months prior to Baseline Visit. PAH therapy which is stopped and then restarted or has dose changes which are not related to initiation and uptitration will be allowed within 3 months prior to the Baseline Visit.
- Hormone therapy.
- Use of warfarin or other anticoagulant (use of aspirin is permitted).
- Platelet count <100,000.
- Renal failure (creatinine \geq 2.0).
- Child-Pugh Class C cirrhosis.
- Current or recent (< 6 months) chronic heavy alcohol consumption.
- Current use of another investigational drug (non-FDA approved) for PAH.

ENDPOINTS:

- Changes in right ventricular systolic pressure, right ventricular fractional area, stroke volume index and tricuspid annular plane systolic excursion
- Changes in six-minute walk distance
- Changes in plasma NT-proBNP and estradiol levels
- Assess safety and side effects associated with fulvestrant administration in subjects with pulmonary arterial hypertension

STUDY OBSERVATIONS:

- Subjects will be evaluated in person at screening, baseline, two weeks, four weeks, eight weeks and nine weeks.
- Subjects will have telephone follow-up at week twelve.
- Laboratory tests including a complete blood count, hepatic function panel, follicle-stimulating hormone, coagulation studies (PT/INR) will be performed at the screening visit.
- Research laboratories such as estradiol (E2) and NT-proBNP levels will be evaluated at baseline and repeated after nine weeks of fulvestrant administration.
- Subjects will have six minute walk testing at baseline and week nine.
- Subjects will have a transthoracic echocardiogram at screening or baseline and week nine.

SAMPLE SIZE AND POWER:

A total of 5 subjects will be enrolled to receive fulvestrant at baseline, two weeks, four weeks, and eight weeks. Formal power calculations were not performed as this study is intended to show feasibility and for hypothesis-generation.

DATA ANALYSIS:

The study endpoints will be evaluated using summary statistics and graphical tools. Univariate analysis will be performed for all variables of interest. These will be carried out by comparing the changes from baseline using signed rank tests for continuous variables and McNemar's test for categorical variables.

Brief Table of Contents

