1.2 Hormonal effects on the vasculature

In PAH, abnormal endothelial cell proliferation and expression of angiogenesis markers characterize the pulmonary vascular lesions. Animal models and patients with PAH have increased pro-angiogenic hematopoietic progenitor cells (HPCs) in the bone marrow and circulating in blood.¹ Estradiol stimulates HPC mobilization via the estrogen receptor α (ER α), and ER α blockade reduces HPC colony formation and endothelial growth.

Estradiol is metabolized by cytochrome P450 (CYP) enzymes to metabolites which have both pro-angiogenic (16 α -OHE1, signaling via ER α) and anti-angiogenic (2-OHE, 2-methoxyestradiol [2ME]) effects. The rs1800440 single nucleotide polymorphism (SNP) in CYP1B1 (enzyme that metabolizes estrone) produces a higher urinary 16 α -OHE1/2-OHE ratio, and both the SNP and urinary ratio are risk factors for heritable PAH.²

Androstenedione and testosterone are converted by aromatase to estrone and estradiol (E2) which signal via ER α and β . Female sex and estrogen are traditionally thought to have beneficial effects on the lung vasculature. Estrogen attenuates pulmonary vascular remodeling and right ventricular changes in hypoxic and monocrotaline animal models of pulmonary hypertension.³⁻⁵ These findings are however inconsistent with human PAH. First, female sex *increases* the risk of idiopathic and heritable PAH and portopulmonary hypertension.⁶ Austin et al. showed that subjects with certain genotypes of CYP1B1 had lower 2-hydroxyestrone:16 α -hydroxyestrone ratio and had a higher risk of PAH.² We have shown that SNPs in aromatase raised circulating E2 levels and increased the risk of PAH.⁷

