7.4 Sample size and power calculations

Formal power calculations have not been performed. This study is intended for hypothesis generation and to show feasibility.

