9.5 Other events

We will not discontinue study drug for clinical events not thought to be serious drug-related AEs. For example, a hospitalization for clinical worsening will not result in cessation of trial participation. Such events could result in missing data for primary and secondary endpoints, comprising the integrity of the analysis. As the trial does not prohibit any therapies which is the standard of care in PAH, there is no ethical or safety reason to stop trial participation under such circumstances. Even if subjects are withdrawn from the study drug outcome assessments will continue. Subjects who are not compliant or stop the treatment portion of the study will be replaced.

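### Whether a PAH admission counts as an adverse event rests on an undefined, open-label investigator judgement, and an admission classed as exempt has no place in the planned safety summary

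*Combined protocol and SAP*

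**What the plan says.** The Protocol Summary describes a "Phase II single-arm, open-label study of fulvestrant in five post-menopausal women with pulmonary arterial hypertension for twelve weeks". Safety and side effects are both an objective and an endpoint.

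Section 9.6.1 defines an AE broadly, to include anything that worsens during the study, and makes an AE serious if it "requires or prolongs hospital stay". Section 9.6.3 repeats that an AE leading to hospitalization is a serious AE (SAE), but lets that rule give way where the protocol instructs otherwise. It then does so: "Neither the condition, hospitalization, prolonged hospitalization, nor surgery are reported as an AE in the following circumstances". One of the listed circumstances is "Hospitalization or prolonged hospitalization for therapy of the target disease of the study, unless it is a worsening or increase in frequency of hospital admissions", and the sentence ends by leaving the decision to the clinical investigator.

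Earlier in 9.6.3, the preexisting-condition rule says that such a condition is recorded as an AE if its frequency, intensity or character worsens. That rule does not mention investigator judgement.

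Section 4.2 places no constraint on PAH medication during the study. Section 9.5 foresees PAH admissions: "a hospitalization for clinical worsening will not result in cessation of trial participation". Section 7.7 plans summaries of the incidence and grade of toxicities and names no table of hospitalizations.

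**The concern.** An admission to start or escalate PAH treatment is, on its plain wording, a stay for therapy of the target disease. Whether it enters the safety data depends on whether the investigator calls it a worsening or a rise in admissions. The protocol gives no criterion for either and does not say whether the disease, the admission pattern or both must worsen. It provides no independent adjudication, and section 8.1 makes the principal investigator and research staff the first line of safety monitoring. In an open-label single-arm trial, whoever makes the call knows that the subject is on fulvestrant.

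If the admission is classed as exempt, neither the stay nor the condition is an AE. The AE form and the severity and relatedness classification in 9.6.2 are then not required, and the event does not reach the section 7.7 summary. At stake is whether the safety statement reflects what happened to the subjects or how one admission was classified.

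**Working it through.** The protocol gives no admission rate, event count or power figure for this point ("Formal power calculations have not been performed", section 7.4), so there is no stated figure to reproduce. The check is mainly textual, with arithmetic for scale.

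**Step 1. The rules side by side**

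| Rule | Worsening PAH with admission | Depends on investigator judgement? |
|---|---|---|
| 9.6.1, AE and SAE definitions | AE, and serious because of the stay | Not stated |
| 9.6.3, preexisting condition | AE | Not stated |
| 9.6.3, general hospitalization rule | SAE, unless the protocol instructs otherwise | No, but yields to the exemption |
| 9.6.3, target-disease exemption | Reportable only if judged a worsening or an increase in admissions | Yes |

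All four lead to reporting when the investigator recognises a worsening. They part when the investigator does not: the first two turn on whether the condition worsened, the last on whether someone judged that it did, and it removes the condition together with the stay. The protocol does not say which governs. The third row points to the exemption.

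**Step 2. What one classification does to the reported result**

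Inputs: n = 5 (Protocol Summary: "A total of 5 subjects will be enrolled to receive fulvestrant"), no control arm, no replaced subjects. Exact (Clopper-Pearson) 95% limits:

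- 0/5 = 0%. Lower limit 0. Upper limit 1 − 0.025^(1/5) = 52.2%.
- 1/5 = 20%. Lower limit 1 − 0.975^(1/5) = 0.5%. Upper limit solves (1 − p)^5 + 5p(1 − p)^4 = 0.025, giving 71.6%.

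One admission reclassified moves the observed incidence by 20 percentage points. The intervals overlap widely, so nothing inferential changes.

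**Step 3. How often this could matter (assumed inputs)**

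Let p be the risk that a subject has a worsening PAH admission during the study, and m the share of those admissions classed as exempt. The documents give neither. Assume at most one admission per subject, and independence. Then P(at least one occurs) = 1 − (1 − p)^5 and P(at least one is counted) = 1 − (1 − p(1 − m))^5.

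| p | At least one occurs | Counted, m = 25% | Counted, m = 50% |
|---|---|---|---|
| 5% | 22.6% | 17.4% | 11.9% |
| 10% | 41.0% | 32.3% | 22.6% |
| 20% | 67.2% | 55.6% | 41.0% |

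The chance that an admission occurs and none is counted is the difference between the columns. It runs from 22.6 − 17.4 = 5.2 points (p = 5%, m = 25%) to 67.2 − 41.0 = 26.2 points (p = 20%, m = 50%). With m = 0 nothing is lost.

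**The case against.** The strongest reply is that the feared harm is expressly kept reportable. Damage to the pulmonary circulation would show as worsening PAH, which the exemption carves out and which 9.6.1 and the preexisting-condition rule capture separately. A reader might infer that the protocol drops PAH admissions from the safety data. The documents do not support that: what remains is possible misclassification. This part of the reply stands.

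Other safeguards exist. AEs are reviewed at every visit from baseline and at the week 12 call, as are concomitant medications (Table 1). Functional class is assessed at baseline, week 4 and week 9. An unanticipated problem is reportable under 9.6.4 even if it is not an SAE. An admission should therefore come to the team's notice. These routes do not settle how it is classified, and they do not place it in the safety summary.

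Three further inferences fail:

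- **That an increase in admission frequency cannot be judged.** The subject's own history, taken at screening and baseline, offers some comparison, and frequency is only an alternative trigger.
- **That the protocol itself predicts this harm.** Section 1.2 does say "Estrogen attenuates pulmonary vascular remodeling and right ventricular changes in hypoxic and monocrotaline animal models of pulmonary hypertension", but its next statement calls those findings inconsistent with human PAH, and the section goes on to argue that estrogen raises risk. The direction of effect is unsettled, and the protocol does not rank harms.
- **That section 9.5 compounds the gap.** It concerns stopping study drug and keeping subjects under assessment, which helps ascertainment.

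Finally, the 20-point shift would follow from any single event in five subjects. It reflects the sample size and is not peculiar to this exemption. That is correct, and it is why the figure is offered as descriptive only.

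**Conclusion.** The point holds as a gap in classification and tabulation. The exemption in 9.6.3 makes the recording of a PAH admission depend on an undefined judgement by an investigator who knows the treatment, it is not reconciled with 9.6.1 and the preexisting-condition rule, and the planned summary has no table that would show an exempt admission. In five subjects one such call decides between 0/5 (0 to 52.2%) and 1/5 (0.5 to 71.6%).

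That size assumes exactly five dosed subjects. Section 7.3.1 allows replacement, so the denominator could be larger. How often misclassification would happen is unknown, and the step 3 figures rest wholly on assumed p and m. No efficacy test is affected. This is a cheap improvement to a stated safety endpoint.

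**What to change.** 1. In 9.6.3, remove the investigator-judgement exemption for PAH admissions that were not planned before enrolment.
2. Reconcile the bullet with 9.6.1 and the preexisting-condition rule, so that any admission in which PAH treatment is started or intensified because of deterioration is recorded as an SAE. Record relatedness separately on the 9.6.2 scale.
3. Give planned medical PAH admissions their own exemption wording. The existing elective bullet covers only diagnostic or surgical procedures, so it would not protect them once the target-disease bullet is narrowed.
4. In 7.7, add a listing and table of every hospitalization with its reason, for all dosed subjects including those replaced, whatever its AE status, over the 9.6.3 reporting period (first study procedure to week 12).

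Deciding whether deterioration prompted an admission still needs some judgement. Item 4 does not depend on it, so it is the most important safeguard.

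The cost is a few lines of text, one short table, a few more forms and possibly a less favourable SAE count. No visit, procedure or sample size changes.
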